9.2.3 Analysis of the Secondary Endpoints

The secondary endpoints include:

- The proportion of subjects with HIV-1 RNA < 50 copies/mL at Week 48 as defined by the US FDA Snapshot Algorithm.
- The proportion of subjects with plasma HBV DNA < 29 IU/mL at Week 48 using the missing = failure method.
- Change from baseline in CD4 cell count and percentage at Week 24 and at 48.
- Proportion of subjects with normalized ALT at Week 24 and Week 48.
- Proportion of subjects with HBV e antigen (HBeAg) loss and seroconversion to anti-HBe at Week 24 and Week 48.
- Proportion of subjects with HBV surface antigen (HBsAg) loss and seroconversion to anti-HBs at Week 24 and Week 48.
- Change from baseline in Fibroscan test score at Week 24 and Week 48.

9.2.4 Safety Analyses

All safety analysis will be performed using the intention-to-treat population. All safety data collected on or after the date, that the study drug was first administered up to the end of the subject's study participation will be summarized for the subject in the safety analysis.

The primary safety endpoint is the proportion of subjects who discontinues study drug due to an adverse event.

There is no formal stopping rule for this trial. The toxicity data will be monitored closely through the therapy. Addressing the safety of FDC B/F/TAF, a maximum width 95% confidence

interval (CI) for any adverse event, grade 3 or higher toxicity will be about 28%. For 50 patients on the study, if the true unknown probability of a rare toxicity is 0.05 (5%), the probability of observing one or more toxicities is 0.92 (92%), and for 3% true toxicity rate, it is 78%.

9.2.5 Baseline Descriptive Statistics

Demographics and other baseline characteristics will be summarized by treatment group.

9.2.6 Planned Interim Analyses

No interim analyses are planned for this study.

9.2.7 Subgroup Analyses

For subgroup analyses, the analysis of the efficacy endpoints will be performed and stratified based on age group, sex, race, baseline CD4 count, HBV DNA viral load, baseline HBeAg status, and baseline HBsAg level.

9.2.8 Exploratory Analyses

Exploratory analyses will include assessment of changes in quantitative HBsAg and immune activation markers during study drug treatment. Immune markers includes plasma hsCRP, IL-6, TNF- α , and D-dimer and cellular HLA-DR+CD38+ CD4 and CD8 T lymphocytes. The exploratory analyses will determine group difference in the exploratory endpoints from baseline (Day 1) to Week 24 and Week 48 time points using a paired t-test. All inferential tests will be indicated statistical significance with a P-value of less than 0.05 (two-sided).

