2.3 Exploratory Objectives

- Evaluate changes in quantitative HBsAg levels during treatment with FDC B/F/TAF.
- Evaluate any changes in immune activation markers (plasma hsCRP, IL-6, TNF- α , and D-dimer and cellular HLA-DR+CD38+ CD4 and CD8 T lymphocytes) during treatment with FDC B/F/TAF.

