2.6 Exploratory Endpoints

[figure not shown]
- Change from baseline in quantitative HBsAg at Week 24 and Week 48.
- Assessment of changes in immune activation markers (plasma hsCRP, IL-6, TNF- α , and D-dimer and cellular HLA-DR+CD38+ CD4 and CD8 T lymphocytes) during treatment with FDC B/F/TAF.

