3.2.3 Treatment Assessments

3.2.3.1 Week 4 and 8 Visits (\pm 7 days)

- Obtain interval medical history.
- Conduct targeted physical examination (if needed), including weight and vital signs [BP, R, HR, T].
- Collect concomitant medication information.
- Collect adverse event information.
- Evaluate Patient Diary and number of used and unused tablets.
- Plasma HIV-1 RNA.
- Plasma HBV DNA.
- Quantitative HBsAg level.
- Complete blood count.
- Comprehensive metabolic panel.
- Urine pregnancy test for women of childbearing potential.
- Blood for storage of plasma, serum, and PBMCs.
- Dispense study drug supply (30-day supply for Week 4; 60-day supply for Week 8).
- Reinforce study drug instruction: subjects are to take one (1) tablet of B/F/TAF once daily upon awakening with at least 8 oz. of plain water, and without regards to food.
- Instruct subject to bring all study drugs and bottles to each future study visits.

3.2.3.2 Week 12, 24, and 36 Visits (\pm 2 weeks for Week 12 and Week 36; \pm 4 weeks for Week 24)

- Obtain interval medical history.
- Conduct targeted physical examination (if needed), including weight and vital signs [BP, R, HR, T].
- Collect concomitant medication information.
- Collect adverse event information.
- Evaluate Patient Diary and number of used and unused tablets.
- Plasma HIV-1 RNA.
- Plasma HBV DNA.
- Quantitative HBsAg level.
- CD4 cell count.
- Complete blood count.
- Comprehensive metabolic panel.
- Urine pregnancy test for women of childbearing potential.
- Blood for PAXgene RNA analysis.
- Blood for storage of plasma, serum, and PBMCs.

- Dispense study drug supply (90-day supply).
- Reinforce study drug instruction: subjects are to take one (1) tablet of B/F/TAF once daily upon awakening with at least 8 oz. of plain water, and without regards to food.
- Instruct subject to bring all study drugs and bottles to each future study visits.

Additional Week 24 assessments:

- HBV profile.
- FibroScan test (IHV only). This test may be done during the Week 24 visit, or within 2 weeks (before or after) the scheduled Week 24 visit.

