9.2.2.2 Missing = Failure Method for HBV Efficacy Analyses

Similarly, the analysis window at Week 24 for HBV DNA outcomes is defined as from Study Day 140 to Day 196. For HBV DNA analysis, this study will use the missing = failure method. HBV virologic outcome will be defined as follows:

- **HBV Virologic Success:** this includes subject who have the last available HBV DNA <29 IU/mL in the Week 24 analysis window while on study treatment.
- **HBV Virologic Failure:** this includes subjects who
 - a. Have the last available HBV DNA \geq 29 IU/mL in the Week 24 analysis window while on study treatment, or
 - b. Do not have on-treatment HBV DNA data in the Week 24 analysis window regardless of reason (e.g. discontinued study drug due to AE, death or lack of efficacy; missed Week 24 visit; withdrew consent for any reason).

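### The planned paired t-tests on quantitative HBsAg leave the Week 4, 8, 12 and 36 values out of any named analysis, and can be biased if subjects who leave differ in their early HBsAg course

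*Combined protocol and SAP*

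**What the plan says.** The exploratory objective in Section 2.3 is to "Evaluate changes in quantitative HBsAg levels during treatment with FDC B/F/TAF". Section 2.6 gives the endpoint as "Change from baseline in quantitative HBsAg at Week 24 and Week 48".

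The assay is collected more often than the endpoint needs. "Quantitative HBsAg level" is in the list for the "Week 4 and 8 Visits" (3.2.3.1) and in the list for the "Week 12, 24, and 36 Visits" (3.2.3.2). It also appears on Day 1 (3.2.2), at Week 48 (3.2.3.3) and in Appendix A.

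Section 9.2.8 names one method, a comparison "from baseline (Day 1) to Week 24 and Week 48 time points using a paired t-test", and adds: "All inferential tests will be indicated statistical significance with a P-value of less than 0.05 (two-sided)". The only other stated use of HBsAg level is as a baseline subgroup factor (9.2.7).

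The missing-data rules do not reach this endpoint. Section 9.2.2.1 applies the Snapshot algorithm to HIV-1 RNA, and 9.2.2.2 says: "For HBV DNA analysis, this study will use the missing = failure method". Both concern binary outcomes.

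**The concern.** A paired t-test can use only subjects who have both values of the pair. Since no rule covers missing HBsAg, a subject without a Week 48 value is absent from the Week 48 comparison, whatever was measured at Weeks 4 to 36. The same holds for Week 24.

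The mean change among those who remain estimates the mean change of all treated subjects only if remaining is unrelated to the HBsAg course. If subjects with a poorer early decline leave more often, the remaining pairs show too large a decline. There is no control arm in which the same selection could partly cancel. The intermediate values that would allow an adjustment are already scheduled.

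**Working it through.** **Plan figure.** The plan gives no power, precision, SD or dropout figure for HBsAg. Its one power figure concerns HIV-1 suppression at Week 24: at least 53 of 60 successes gives exact power of 83.1%, against 84% stated. It has no bearing on this point.

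**Inputs.** N = 60 (Section 5.1) and the visit schedule (Appendix A) come from the plan. The rest is assumed: log10 scale, straight-line individual courses with slope SD 0.25 per 48 weeks, residual SD 0.12, dropout after Week 12 with baseline probability p of 10–20%.

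**Step 1: variances.** Write D12 and D48 for the changes from Day 1 to Weeks 12 and 48.
- Var(D48) = 0.25² + 2 × 0.12² = 0.0625 + 0.0288 = 0.0913; SD 0.302. With all 60 subjects the SE is 0.302/√60 = 0.039.
- Var(D12) = (0.25/4)² + 0.0288 = 0.0039 + 0.0288 = 0.0327; SD 0.181.
- Cov(D12, D48) = 0.0625/4 + 0.12² = 0.0156 + 0.0144 = 0.0300.
- One SD of D12 shifts the expected D48 by 0.0300/0.181 = 0.166. The correlation is 0.0300/(0.181 × 0.302) = 0.549, so R² = 0.302.

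**Step 2: no dropout.** A model with categorical visit and unstructured covariance gives the same change and the same SE as the paired comparison.

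**Step 3: dropout unrelated to response.** Neither estimate is biased. Using D12 alone to recover information on the lost subjects, the ratio of paired to model variance is 1/(1 - p × R²):
- p = 10%: 1/(1 - 0.0302) = 1.03
- p = 20%: 1/(1 - 0.0604) = 1.06

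Simulation with all earlier visits and an estimated unstructured covariance gave about 1.04–1.08, the same order. Treating the covariance as known overstates the gain: seven visits need 7 × 8/2 = 28 covariance parameters from about 60 subjects.

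**Step 4: dropout related to early response.** Let z be the standardised D12, higher meaning a poorer decline, and logit P(leave) = logit(p) + γz. Then bias of the paired Week 48 change = 0.166 × E(z | stays), with the expectation integrated over a standard normal z. The paired SE is √(0.0913/(60 × proportion staying)).

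| p | γ | leave | E(z, stays) | bias (log10) | paired SE | bias/SE |
|---|---|---|---|---|---|---|
| 10% | 0.25 | 10.2% | -0.025 | -0.004 | 0.041 | 0.1 |
| 10% | 0.5 | 10.9% | -0.053 | -0.009 | 0.041 | 0.2 |
| 10% | 1 | 13.4% | -0.119 | -0.020 | 0.042 | 0.5 |
| 20% | 0.25 | 20.3% | -0.050 | -0.008 | 0.044 | 0.2 |
| 20% | 0.5 | 21.1% | -0.102 | -0.017 | 0.044 | 0.4 |
| 20% | 1 | 23.9% | -0.204 | -0.034 | 0.045 | 0.8 |

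Simulation reproduces this range, with bias of the all-visit estimate close to zero. At γ = 1 the simulated variance ratio is about 0.98–1.00, so there is no reliable precision gain there.

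**Step 5: sensitivity to the assumptions.** A second simulation used residual SD 0.10, half of the dropouts leaving after Week 12 and half after Week 24, and steeper selection (sampling weight exp(1.5) per SD of a poorer Week 12 change). At 10/20/30% dropout the paired SE was 2/6/8% larger under random loss. Under selective loss the bias was -0.022/-0.041/-0.061, which is 0.6/1.0/1.4 of the paired SE (0.039/0.041/0.042). Size therefore depends heavily on how strong and how frequent selective loss is taken to be.

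**The case against.** The strongest reply is that the test matches the endpoint. Section 2.6 asks for change at two visits, and a paired t-test estimates exactly that. The plan nowhere says that other values will be discarded, and descriptive use is not ruled out. This stands: the point is that no named analysis uses them.

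A reader might infer that a subject needs all three of the Day 1, Week 24 and Week 48 values. The wording of 9.2.8 does not support this. The pairs are separate, so a subject missing only Week 48 still counts at Week 24.

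Selective loss is also partly guarded against. Section 3.2.4 asks subjects who stop study drug to keep attending through Week 48 unless consent is withdrawn, and early leavers receive the Week 48 assessments, which include quantitative HBsAg (3.2.3.3; Appendix A, note g). HBsAg is not itself a discontinuation criterion in 3.2.5, and about 87% of the source clinics' coinfected patients already take tenofovir (Section 1.1), so strong sorting by early HBsAg response to the switch is not established.

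These points reduce the problem but do not remove it. Subjects who withdraw consent or are lost still have no later value. An early-termination value is not a Week 24 or Week 48 value unless a rule makes it one. Values after stopping drug raise a further question that 9.2.8 leaves open: whether they count towards change during treatment.

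Finally, the near-zero bias of the model is built into the simulations, because dropout there depends only on observed values. That too stands.

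**Conclusion.** The point holds as an inexpensive improvement to an exploratory analysis. The paired tests leave four scheduled on-treatment visits unused and have no stated protection against selective loss. With complete data the estimate would be unchanged.

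Under the main assumptions the precision cost is single-digit in variance. The Week 48 bias runs from negligible to about 0.8 SE; only the harsher case in Step 5 exceeds that.

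Two stronger readings should be resisted. One is that the plan will overstate the HBsAg decline; the documents give no dropout rate or mechanism that would show this. The other is that the bias is a known share of the true effect. The bias in Step 4 does not depend on the true change, which the documents do not give, so any percentage reflects the effect size chosen.

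Nothing here touches the primary endpoints or the sample size.

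**What to change.** In 9.2.8, make a linear mixed model for repeated measures the main analysis of quantitative HBsAg:
- all scheduled visits from Day 1 to Week 48, with visit as a categorical effect;
- unstructured within-subject covariance, with a named simpler structure if the model does not converge;
- model-based change at Week 24 and Week 48, each with a 95% confidence interval;
- the missing-at-random assumption stated;
- a statement of whether values after stopping study drug are included.

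Keep the paired t-test as a supportive analysis. Use the same model for an immune marker only if that marker is assayed at more than two visits; Appendix A does not list marker visits separately.

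The cost is a few lines of text and slightly more analysis work, with no new visits, samples or assays. The downside is reliance on missing at random, which the data cannot verify; the model does not remove bias if leaving depends on unobserved values.

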10 ADMINISTRATIVE, ETHICAL, AND REGULATORY CONSIDERATIONS

10.1 Informed Consent Process

Informed consent is a process that is initiated prior to the individual agreeing to participate in the study and continues throughout the individual's study participation. The informed consent form will be IRB-approved and the participant will be asked to read and review the document. The investigator is responsible for presenting the risks and benefits of study participation to the subject in simple terms using the informed consent document. The investigator will ensure that written informed consent is obtained from each subject or legally authorized representative by obtaining the appropriate signatures and dates on the informed consent document before the performance of protocol evaluations or procedures.

Participants must be informed that participation is voluntary and that they may withdraw from the study at any time, without prejudice. Copies of the informed consent documents will be given to the participants for their records. The informed consent process will be conducted and documented in the source document (including the date), and the screening form signed, before the participant undergoes any study-specific procedures. The rights and welfare of the participants will be protected by emphasizing to them that the quality of their medical care will not be adversely affected if they decline to participate in this study.

Additionally, employees or students will be made aware that employment status or academic standing will not be affected by your participation or non-participation in this study. Students or employees will not be consented by anyone in a supervisory role.

As the majority of the patient populations from which the study participants are drawn are literate, written informed consent will typically be provided during the informed consent process. However, oral consent will be obtained for illiterate participants as consistent with UMB IRB Policy without separate IRB approval for each specific use. At Continuing Reviews, the UMB IRB will be informed of the number of illiterate participants who provided consent verbally. A non-study team witness will be present for the oral consenting process.

10.2 Study Discontinuation and Closure

This study may be suspended or prematurely terminated if there is sufficient reasonable cause. The suspending or terminating party will provide written notification, documenting the reason for study suspension or termination, to the study participants, investigator, funding agency, the Investigational New Drug (IND) sponsor, and regulatory authorities in a timely manner. If the study is prematurely terminated or suspended, the Investigator will promptly inform study

participants, the IRB, and sponsor, and he will provide the reason(s) for the termination or suspension. Study participants will be contacted, as applicable, and be informed of changes to study visit schedule.

Circumstances that may warrant termination or suspension include, but are not limited to:

- Determination of unexpected, significant, or unacceptable risk to participants
- Demonstration of efficacy that would warrant stopping
- Insufficient compliance to protocol requirements
- Data that are not sufficiently complete and/or evaluable
- Determination that the primary endpoint has been met
- Determination of futility

Study may resume once concerns about safety, protocol compliance, and data quality are addressed, and satisfy the sponsor, DSMB, IRB and/or Food and Drug Administration (FDA) as appropriate.

10.3 Confidentiality and Privacy

Participant confidentiality and privacy is strictly held in trust by the participating investigators, their staff, and the sponsor. This confidentiality is extended to cover testing of biological samples and genetic tests in addition to the clinical information relating to participants. Therefore, the study protocol, documentation, data, and all other information generated will be held in strict confidence. No information concerning the study or the data will be released to any unauthorized third party without prior written approval of the sponsor.

All research activities will be conducted in as private a setting as possible.

The study monitor, other authorized representatives of the sponsor, representatives of the IRB, regulatory agencies or pharmaceutical company supplying study product may inspect all documents and records required to be maintained by the investigator, including but not limited to, medical records (office, clinic, or hospital) and pharmacy records for the participants in this study. The clinical study site will permit access to such records.

The study participant's contact information will be securely stored at each clinical site for internal use during the study. At the end of the study, all records will continue to be kept in a secure location for as long a period as dictated by the reviewing IRB, Institutional policies, or sponsor requirements.

Study participant research data, which is for purposes of statistical analysis and scientific reporting, will be entered into the electronic database for future analysis. This will not include the participant's contact or identifying information. Rather, individual participants and their research data will be identified by a unique study identification number. The study data entry and study management systems used by the IHV research staff will be secured and password protected. At the end of the study, all study databases will be de-identified and archived at the IHV.

10.4 Future Use of Stored Specimens and Data

Data collected for this study will be analyzed and stored at University of Maryland, Institute of Human Virology. With the participant's approval within the consent and as approved by local IRB, de-identified biological samples may be shared with Gilead Sciences, Inc. with the goal of sharing of data. These samples could be used to research immune response to HBV, its complications and other conditions for which individuals with HBV are at increased risk, and to improve treatment. Gilead Sciences, Inc. will also be provided with a code-link that will allow linking the biological specimens with the phenotypic data from each participant, maintaining the blinding of the identity of the participant.

During the conduct of the study, an individual participant can choose to withdraw consent to have optional biological specimens for future research stored, in which case they will be destroyed.

When the study is completed, access to study data and/or samples will be provided by [name].

10.6 SAFETY OVERSIGHT

Safety oversight will be under the direction of a Safety Monitoring Committee (SMC) composed of individuals with the appropriate expertise, including experience with the treatment and/or care of those with HIV-1 and HBV. At least two members of the SMC will be independent from BEST-HBV Protocol Version 4.0: March 16, 2021

the study conduct and free of conflict of interest, or measures should be in place to minimize perceived conflict of interest. The SMC will meet at least semiannually to assess safety and efficacy data. The SMC will provide its input to the study sponsor and Principal Investigator.

10.7 Clinical Monitoring

Clinical site monitoring is conducted to ensure that the rights and well-being of trial participants are protected, that the reported trial data are accurate, complete, and verifiable, and that the conduct of the trial complies with the currently approved protocol/amendment(s), with ICH GCP, and with applicable regulatory requirement(s).

Monitoring will begin as the first two subjects screen for the clinical trial. This will entail a clinical research nurse providing 100% verification of screening consent and data verification of the first 2 subjects. An independent SMC member will be available for consultation as needed for any medical concerns.

Once subjects begin enrollment, consent and eligibility verification will continue at 100%, with 15% targeted subject data review.

10.8 Data Handling and Record Keeping

10.8.1 Data Collection and Management Responsibilities

All research data and results will be recorded using data collection forms. Source documents will support the data collected and will include, but not limited to; clinical findings and observations, laboratory and test data, hospital medical records, physician or office charts, physician or nursing notes, recorded data from automated instruments, x-rays, etc. Research data will be entered into a secure electronic database. This electronic database tracks all data corrections made by authorized users, providing audit trails for monitoring or query.

10.8.2 Study Records Retention

The investigator is responsible for retaining all essential documents listed in the ICH GCP Guideline. All essential documentation for all study subjects are to be maintained by the investigators in a secure storage facility for a minimum of 5 years. The FDA requires study records to be retained for up to 2 years after marketing approval or disapproval (21 CFR 312.62), or until at least 2 years have elapsed since the formal discontinuation of clinical development of the investigational agent for a specific indication. These records are also to be maintained in compliance with IRB, state, and federal medical records retention requirements, whichever is longest. All stored records are to be kept confidential to the extent required by federal, state, and local law.

